### 3.11 Discontinuation of the study

The study may be stopped if, in the judgment of AstraZeneca, trial participants are placed at undue risk because of clinically significant findings that:

- Meet individual stopping criteria or are otherwise considered significant,
- Are assessed as causally related to study intervention,
- Are not considered to be consistent with continuation of the study.

Regardless of the reason for termination, all data available for the participant at the time of discontinuation of follow-up must be recorded in the eCRF. All reasons for discontinuation of treatment must be documented.

In terminating the study, the Sponsor will ensure that adequate consideration is given to the protection of the participants' interests.

Redacted for Public Disclosure

## 4 STUDY PLAN AND TIMING OF PROCEDURES

The Study plan detailing the procedures at screening, during the treatment and follow-up period are presented in [Table 3](#), [Table 4](#) and [Table 5](#).

### 4.1 Study plan

**Table 3** Study plan detailing the procedures at Screening

Study Period	Screening	Details in Section
Written informed consent /assignment of E#	X	10.4
Medical history a	X	5.1.4
Complete physical examination, weight and height	X	5.2.2
Vital signs	X	5.2.3
ECG	X	5.2.2.5
Serum chemistry, haematology, and urinalysis	X	5.2.1
Urine protein/creatinine ratio	X	5.2.1
ANA, anti-dsDNA antibodies, anti-Sm antibody b	X	5.4.3
B cell count c	X	5.2.1
Chest X-ray (only in participants who have not had a chest radiograph within 12 weeks prior to signing the ICF) d	X e	5.2.6.1
FSH in postmenopausal females	X	5.2.1
Serum pregnancy test in all females of childbearing potential	X	5.2.1
Blood test for TB f	X	5.2.6.1
Hepatitis B and C	X	5.2.1
HIV test	X	5.2.1
COVID-19 test and COVID-19 questionnaire	X	5.2.7
Cervical Cancer Screening Test (HPV/Pap smear) i	X e	5.2.1
C3, C4, CH50 complement	X	5.2.1
BILAG-2004 associated laboratory tests (anticardiolipin, lupus anticoagulant, haptoglobin, and Coombs g )	X	5.2.1
C-SSRS	X	5.2.5
BILAG-2004	X h	5.1.4
CLASI	X h	5.1.8
SLEDAI-2K	X h	5.1.3
PGA	X h	5.1.5
Joint count	X h	5.1.9
TB questionnaire	X	5.2.6.3
Assessment of AEs/SAEs/AESIs	X	6; 6.3; 6.6
ACR classification criteria	X	Appendix D
Concomitant medications, including SLE medications	X	7.7
Verify eligibility criteria	X	3.1; 3.2

ACR = American College of Rheumatology; AE = adverse event; AESI = adverse event of special interest; ANA = antinuclear antibody; anti-Sm= Anti-Smith; BILAG = British Isles Lupus Assessment Group; C3 = third component of complement; C4 = fourth component of complement; CH50 = total hemolytic complement; CLASI = Cutaneous Lupus Erythematosus Disease Area and Severity Index; C-SSRS = Columbia Suicide Severity Rating Scale; CT = computed tomography; dsDNA = Double stranded deoxyribonucleic acid; ECG = electrocardiogram; FSH = Follicle-stimulating hormone; HIV= Human immunodeficiency virus; HPV= Human Papilloma Virus; IGRA =Interferon-gamma release assay; PGA = Physician's Global Assessment; QFT-G= QuantiFERON®-TB Gold In-Tube; SAE = serious adverse event; SLE =Systemic lupus erythematosus; SLEDAI-2K = Systemic Lupus Erythematosus Disease Activity Index 2000; TB = tuberculosis

aMedical History will include details for each body system contained in the BILAG-2004 assessment (BILAG Related History)

bRedraw for ANA and anti-dsDNA can be done within the 35 days screening window, however, results must be available within the 35 days screening window for participants to be randomised.

cReceipt of B cell-depleting therapy (including but not limited to, ocrelizumab, ofatumumab, atacicept, obinutuzumab, or rituximab) < 26 weeks prior to signing the ICF (< 40 weeks for atacicept), and if therapy was administered  $\geq$  26 weeks ago (40 weeks for atacicept), absolute B cell less than the lower limit of normal or baseline value prior to receipt of B cell-depleting therapy (whichever is lower).

dAnterior- posterior, and lateral images are required whenever possible, or per standard of care.

eAssessments required to determine eligibility and stratification are allowed anytime during the screening period as long as they are completed within 35 days after signing the ICF.

fInterferon-gamma release assay (IGRAs) using QuantiFERON®-TB Gold In-Tube (QFT-G) Test

gDirect Coombs test samples will only be collected per Investigator's opinion, measured by local laboratory, and applicable BILAG assessment requirements for determining haemolytic anaemia.

hThese assessments must all be completed at the same visit (SLEDAI-2K, BILAG-2004, joint count, PGA, and CLASI).

iFemale participants with an intact cervix should have a Cervical Cancer Screening Test (HPV/Pap smear) within 2 years prior to randomization (unless female < 25 years old which is specified in Exclusion Criteria #21). Since access to a HPV/Pap smears may vary by county, the Sponsor recommends that local guidelines for obtaining HPV/Pap smears in participants who have received immunomodulators or immunosuppressive treatment be followed.

**Table 4 Study plan detailing the procedures during the Treatment Period (double-blind period)**

Visit Number	V1 a	V2	V3	V4	V5	V6	V7	V8	V9	V10	V11	V12	V13	V14 (EOT-DB)	EDV-DB o	Details in Section
Study Week	W0	W4	W8	W12	W16	W20	W24	W28	W32	W36	W40	W44	W48	W52	NA	NA
Procedure/Visit Window		±7D	±7D	±7D	±7D	±7D	±7D	±7D	±7D	±7D	±7D	±7D	±7D	±7D	NA	NA
EQ-5D-5L, Lupus QoL, WPAI	X			X			X			X				X	X	5.3.1 5.3.3 5.3.4
Medical history	X															5.1.4
Complete physical examination	X						X							X	X	5.2.2.1
Focused physical examination		X	X	X	X	X		X	X	X	X	X	X			5.2.2.2
Weight Assessment of Cushingoid features	X	X	X	X	X	X	X	X	X	X	X	X	X	X	X	5.2.2
ECG	X						X							X	X	5.2.2.4
Vital signs	X	X	X	X	X	X	X	X	X	X	X	X	X	X	X	5.2.2.5 5.2.3
Serum chemistry, haematology, and urinalysis	X	X	X	X	X	X	X	X	X	X	X	X	X	X	X	5.2.1

Visit Number	V1 a	V2	V3	V4	V5	V6	V7	V8	V9	V10	V11	V12	V13	V14 (EOT-DB)	EDV-DB o	Details in Section
Study Week	W0	W4	W8	W12	W16	W20	W24	W28	W32	W36	W40	W44	W48	W52	NA	NA
Procedure/Visit Window		±7D	±7D	±7D	±7D	±7D	±7D	±7D	±7D	±7D	±7D	±7D	±7D	±7D	NA	NA
Cervical cancer screening (HPV/Pap smear)														X b	X b	5.2.2.3
Urine pregnancy test c	X	X	X	X	X	X	X	X	X	X	X	X	X	X	X	5.2.1
TB blood test (QFT-G)				X d			X d							X	X	5.2.6.1
HBV DNA m				X			X			X			X			3.2
Immunology profile k	X						X							X	X	5.2.1.1
Lipid profile e	X						X							X	X	5.2.1.1
Cardiovascular risk assessment	X													X	X	5.2.4
IFN-γ gene sample collection f	X															5.4.4
PK blood sample (predose) g	X	X		X			X			X			X	X	X	5.4.1

Visit Number	V1 a	V2	V3	V4	V5	V6	V7	V8	V9	V10	V11	V12	V13	V14 (EOT-DB)	EDV-DB o	Details in Section
Study Week	W0	W4	W8	W12	W16	W20	W24	W28	W32	W36	W40	W44	W48	W52	NA	NA
Procedure/Visit Window		±7D	±7D	±7D	±7D	±7D	±7D	±7D	±7D	±7D	±7D	±7D	±7D	±7D	NA	NA
PK blood sample (postdose) g	X												X			5.4.1
Immunogenicity blood sample (predose) n	X			X			X			X			X	X	X	5.4.3
SLEDAI-2K associated laboratory tests h	X	X	X	X	X	X	X	X	X	X	X	X	X	X	X	5.2.1
■	■	■		■			■			■			■	■	■	5.4.2.1
(PD marker) i																
C-SSRS	X	X	X	X	X	X	X	X	X	X	X	X	X	X	X	5.2.5
BILAG-2004	X	X	X	X	X	X	X	X	X	X	X	X	X	X	X	5.1.4
BILAG-2004 associated laboratory tests j	X	X	X	X	X	X	X	X	X	X	X	X	X	X	X	5.2.1
CLASI	X	X	X	X	X	X	X	X	X	X	X	X	X	X	X	5.1.8
SLEDAI-2K	X	X	X	X	X	X	X	X	X	X	X	X	X	X	X	5.1.3
SDI	X						X							X	X	5.1.7

Visit Number	V1 a	V2	V3	V4	V5	V6	V7	V8	V9	V10	V11	V12	V13	V14 (EOT-DB)	EDV-DB o	Details in Section
Study Week	W0	W4	W8	W12	W16	W20	W24	W28	W32	W36	W40	W44	W48	W52	NA	NA
Procedure/Visit Window		±7D	±7D	±7D	±7D	±7D	±7D	±7D	±7D	±7D	±7D	±7D	±7D	±7D	NA	NA
PGA	X	X	X	X	X	X	X	X	X	X	X	X	X	X	X	5.1.5
Joint count	X	X	X	X	X	X	X	X	X	X	X	X	X	X	X	5.1.9
Protocol-specified steroid tapering (if indicated)			X	X	X	X	X	X	X	X	X					7.7
Medical Resource Use	X	X	X	X	X	X	X	X	X	X	X	X	X	X	X	5.3.2
Questionnaire TB	X	X	X	X	X	X	X	X	X	X	X	X	X	X	X	5.2.6.3
Assessment of AEs/SAEs/AESIs	X	X	X	X	X	X	X	X	X	X	X	X	X	X	X	6
Concomitant medications	X	X	X	X	X	X	X	X	X	X	X	X	X	X	X	7.7
Verify eligibility criteria	X															3.1, 3.2
Randomisation	X															3.3

Visit Number	V1 a	V2	V3	V4	V5	V6	V7	V8	V9	V10	V11	V12	V13	V14 (EOT-DB)	EDV-DB o	Details in Section
Study Week	W0	W4	W8	W12	W16	W20	W24	W28	W32	W36	W40	W44	W48	W52	NA	NA
Procedure/Visit Window		±7D	±7D	±7D	±7D	±7D	±7D	±7D	±7D	±7D	±7D	±7D	±7D	±7D	NA	NA
Investigational medicinal product administration 	X	X	X	X	X	X	X	X	X	X	X	X	X			7

AE = adverse event; AESI = Adverse Event of Special Interest ; BILAG = British Isles Lupus Assessment Group; CLASI = Cutaneous Lupus Erythematosus Disease Area and Severity Index; C-SSRS = Columbia Suicide Severity Rating Scale (C-SSRS); dsDNA = double stranded deoxyribonucleic acid; ECG = electrocardiogram; EDV = Early Discontinuation Visit; EQ-5D- 5L = EuroQoL 5 dimensions; HBV = hepatitis B virus; HPV = Human Papilloma Virus; IFN = interferon; PD = pharmacodynamic; PGA = Physician's Global Assessment; PK = pharmacokinetic; QFT-G = QuantiFERON® -TB Gold In-Tube; SAE = serious adverse event; SDI = Systemic Lupus International Collaborating Clinics/American College of Rheumatology Damage Index; SLEDAI-2K = Systemic Lupus Erythematosus Disease Activity Index 2000; TB = tuberculosis; WPAI = Work Productivity and Activity Impairment.

aOnce screening assessments needed to confirm eligibility and stratification are complete, all laboratory results are reported, and central review is complete, a participant may be randomised. There does not need to be 35 days between screening and Randomisation (Day 1).

bFemale participants should have a Cervical Cancer Screening Test (HPV/Pap smear) per local standard of care, if possible, between Week 48 and Week 52 to ensure that there is no evidence of new cervical dysplasia (unless female < 25 years old which is specified in Exclusion Criteria #21). Since access to HPV/Pap smears may vary by county, the Sponsor recommends that local guidelines for obtaining HPV/Pap smears in participants who have received immunomodulators or immunosuppressive treatment be followed. For participants who early discontinue investigational medicinal product, and is willing to return for all regularly clinic scheduled visits, the HPV/Pap smear should be done between Week 48 and Week 52.

cUrine pregnancy test in females of childbearing potential.

dOnly for participants with indeterminate QFT-G result at screening but no latent TB treatment is warranted. The QFT-G will be retested at Week 12 and Week 24 for the first 6 months. See section 6.3.5 for more instruction.

eLipid profile (cardiovascular assessment) - participants will be required to fast for at least 8 hours prior to this assessment. If a participant has not fasted, the assessment should be performed under fasted conditions at the next visit.

fSLEDAI-2K associated laboratory tests are C3, C4, CH50 complement, anti-dsDNA antibodies, urine protein/creatinine ratio. If Central laboratory results are not available for SLEDAI-2K associated samples drawn on the date of visit, labs should be redrawn one time within 14 days of SLEDAI-2K assessment date.

gBILAG-2004 laboratory tests to include Coombs (if applicable), anticardiolipin, lupus anticoagulant, haptoglobin. Note: In order to avoid having to bring the participant back for a separate phlebotomy, the blood specimen for anticardiolipin, lupus anticoagulant, haptoglobin will be collected at the specified visits, however the blood will be stored at the central laboratory, and the analyses performed only if Investigator indicates that these tests need to be completed because of clinical suspicion of haemolytic anaemia or

antiphospholipid syndrome. Direct Coombs test samples will only be collected per Investigator's opinion at local laboratory and applicable BILAG assessment requirements for determining haemolytic anaemia.

kImmunology profile includes ANA, anti-Sm, anti-RNP, anti-SSA, and anti-SSB, and quantitative immunoglobulins.

lInvestigational medicinal product will be administered as an IV infusion via an infusion pump over a minimum of 30 minutes.

mParticipants who are HBcAb positive at screening will be tested every 3 months for HBV DNA. To remain eligible for the study, participant's HBV DNA levels must remain below the LLOQ as per central laboratory

n In order to help understand the potential drug-relatedness of any hypersensitivity or anaphylaxis reaction, possible additional ADA testing (if not already scheduled for a visit) may be collected and analysed

oIf the participant is unwilling to complete all regularly scheduled clinic visits, the participant should complete the EDV within 4 weeks of the last dose of investigational medicinal product, as well as Follow-up Visit 1 and Follow-up Visit 2 (8 and 12 weeks after the last dose) unless consent is withdrawn. If the participant is unwilling to continue with any study visits, including EDV visit, at a minimum, the assessments mentioned in section 4.3.1 should be completed.

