**Table 1 Risk for Anifrolumab and Study Procedures**

Potential risk of clinical significance	Summary of data/rationale for risk	Mitigation strategy
Anifrolumab Risks		
Important Identified Risk: Herpes zoster Identified Risks Upper respiratory tract infection, bronchitis, respiratory tract infection, hypersensitivity, anaphylactic reaction, infusion-related reaction a	Refer to the IB for the most up-to-date safety data.	
Patients will be excluded from participation in the study if they have: recurrent or opportunistic infection requiring hospitalization and IV antibiotics; live or attenuated vaccine or clinically significant infection within 8 weeks prior to signing the ICF; history of a primary immunodeficiency, splenectomy, or any underlying condition that predisposes the participant to infection, or a positive HIV result; active HBV, HCV, CMV, or Epstein-Barr virus infection; severe HZ infection; or any infection requiring oral anti-infectives within 2 weeks prior to signing the ICF. See Section 3.2.
 
Infections, including non-opportunistic serious infections, opportunistic infections, TB, and latent TB will be monitored closely in this study. See Section 3.2, Section 5.2.6, and Section 6.3.
 
The incidence of severe allergic reactions has been low after IV administration of anifrolumab. Therefore, appropriate drugs and medical equipment to treat acute anaphylactic reactions will be immediately available, and site staff will be trained to recognize and treat anaphylaxis. See Section 3.2 and Section 6.10.1.

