### 3.9 Discontinuation of study intervention

Participants may be discontinued from investigational medicinal product in the following situations:

1. Participant decision. The participant is at any time free to discontinue treatment, without prejudice to further treatment. The primary reason should be documented as 1 of the following:
  - (a) Participant perceives the investigational medicinal product to be ineffective.
  - (b) Participant is unable to comply with protocol-specified visits and/or procedures due to conflicts not related to clinical trial.
  - (c) Participant perceives logistics to be unacceptable.
  - (d) Participant wishes to participate in another clinical trial.
  - (e) Participant wishes to take a treatment that is not allowed in this study.
  - (f) An AE or laboratory abnormality is of concern to the participant, but not clinically significant to physician.
  - (g) Other, please specify reason.
2. Lost to follow-up
3. AE that, in the opinion of Investigator or the AstraZeneca study physician, contraindicates further dosing with investigational medicinal product.
4. Severe non-compliance with the study protocol.
5. Investigator or the AstraZeneca study physician deems withdrawal as being in the participant's best interest.
6. Pregnancy, positive pregnancy test, non-compliance with protocol-defined contraceptive recommendations or participant expresses an interest to become pregnant.
7. Isolated HBc positivity with HBV DNA confirmed by the central laboratory.
8. Positive HIV test.
9. Confirmed diagnosis of non-cutaneous herpes zoster.
10. Anaphylactic reaction or severe hypersensitivity reaction suspected to be related to IMP.
11. Participants that develop malignancies during the study should be discontinued from IMP. Exception for non-melanoma skin cancers where discontinuation is at the discretion of investigator and/study physician.
12. Receipt of any prohibited medications identified in Section 7.7.1.2.
13. The use of restricted medications listed in Section 7.7.1.3 if, in consultation with the sponsor, the AstraZeneca study physician determines the participant must be discontinued.
14. A diagnosis of active TB, premature discontinuation of treatment for latent TB, or noncompliance with TB therapy. Note: duration of treatment for latent TB should follow

the local practice. If local practice is not defined, then Centres for Disease Control guidance should be used.

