**Table 5 Study plan detailing the procedures during follow-up**

Visit Number	Follow-up Visit 1 a	Follow-up Visit 2 a	Details in Section
Study Week Procedure/Visit Window	8 weeks post last dose ±7D	12 weeks post last dose ±7D	
EQ-5D-5L, WPAI		X	5.3.1; 5.3.4
Complete physical examination, weight		X	5.2.2
Vital signs	X	X	5.2.3
Serum chemistry, haematology, and urinalysis	X	X	5.2.1
Urine pregnancy test in females of childbearing potential	X	X	5.2.1
PK blood sample	X	X	5.4.1
Immunogenicity blood sample d		X	5.4.3
TB questionnaire	X	X	5.2.6.3
SLEDAI-2K associated laboratory tests b	X	X	5.2.1
BILAG-2004 associated laboratory tests c	X	X	5.2.1
C-SSRS	X	X	5.2.5
BILAG-2004	X	X	5.1.4
CLASI	X	X	5.1.8
SLEDAI-2K	X	X	5.1.3
PGA	X	X	5.1.5
Joint count	X	X	5.1.9
Medical Resource Use Questionnaire	X	X	5.3.2
Assessment of AESIs	X	X	6.3; 6.6
Assessment of AEs/SAEs	X	X	6
Concomitant medications	X	X	7.7

AE = adverse event; AESI = Adverse Event of Special Interest; BILAG = British Isles Lupus Assessment Group; CLASI = Cutaneous Lupus Erythematosus; Disease Area and Severity Index; EQ-5D-5L = EuroQoL 5 dimensions; IFN = interferon; PD = pharmacodynamic; PGA = Physician's Global Assessment; PK = pharmacokinetic; SAE = serious adverse event; SLEDAI-2K = Systemic Lupus Erythematosus Disease Activity Index 2000; TB = tuberculosis; WPAI = Work Productivity and Activity Impairment; C-SSRS = Columbia Suicide Severity Rating Scale.

aFollow-up assessments are to be completed when participants complete the study (e.g., early termination or after the treatment period). Participants with early IMP discontinuation do not need to return for further safety follow-up assessments if they have been followed up for at least 12 weeks after the last dose during regularly scheduled clinical visits.

bSLEDAI-2K associated laboratory tests are C3, C4, CH50 complement, anti-ds DNA, urine protein/creatinine ratio. If central laboratory results are not available for SLEDAI-2K associated samples drawn on the date of visit, labs should be redrawn one time within 14 days of the SLEDAI assessment date.

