#### **4.3.1 Follow up visits after premature discontinuation of investigational medicinal product**

**Participants who discontinue investigational medicinal product (see Section 3.9) will be asked to return for all regularly scheduled clinic visits.** If the participant is unwilling to complete all regularly scheduled clinic visits, the participant should complete the EDV within 4 weeks of the last dose of investigational medicinal product, as well as Follow-up Visit 1 and Follow-up Visit 2 (8 and 12 weeks after the last dose) unless consent is withdrawn.

If the participant is unwilling to continue with any study visits, including EDV visit, at a minimum, the following assessments should be completed:

- SLEDAI-2K and the associated laboratory tests (anti-dsDNA antibodies, C3, C4, CH50).
- BILAG-2004 laboratory tests to include anticardiolipin, lupus anticoagulant, haptoglobin and Coombs (Coombs will be performed at local laboratory as applicable per BILAG assessment requirements).
- Note: In order to avoid having to bring the participant back for a separate phlebotomy, the anticardiolipin, lupus anticoagulant, and haptoglobin blood specimen will be collected at all specified visits, however the blood will be stored at the central laboratory, and the analyses performed only if Investigator indicates that these tests need to be completed because of clinical suspicion of haemolytic anaemia or antiphospholipid syndrome. Direct Coombs test samples will only be collected per Investigator's opinion at local laboratory and applicable BILAG assessment requirements for determining haemolytic anaemia.
- CLASI
- PGA
- Joint count

The following safety assessments will also be completed:

- Serum chemistry, haematology, urinalysis
- Urine for protein, creatinine and urine-protein-creatinine ratio
- Lipid Profile defined in Section 5.2.1.1
- Immunology Profile defined in Section 5.2.1.1
- Vital signs
- Complete physical examination, weight
- AE including AESIs
- Cardiovascular risk assessment

- TB questionnaire
- Concomitant medications

If the participant does not agree to do this, they will be asked if they can be followed on a monthly basis via telephone calls until 12 weeks post the last dose of IMP. At these calls, they will be asked about AEs/SAEs, lupus symptoms, and lupus medications. Steroid bursts will also be captured.

Adverse events will be followed up per Section 6.4.2.

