#### **5.2.2.3 Cervical Cancer Screening Test (Pap Smear/HPV Test)**

Most cases of cervical cancer appear to be related to infection with papilloma virus. Because of the potential for viral reactivation due to blockade of the interferon pathway, we are

assessing cervical dysplasia in this study, although to date there has been no signal in the anifrolumab studies.

A Cervical Cancer Screening Test (Pap smear/HPV test which is in align with local practice) is required at screening in women who have not had their cervix surgically removed. If a Cervical Cancer Screening Test was performed within 2 years prior to screening with no documented malignancy (e.g., cervical intraepithelial neoplasia grade III [CIN III], carcinoma in situ [CIS], or adenocarcinoma in situ [AIS]) or no High-risk HPV was found, it does not need to be repeated. Abnormal Cervical Cancer Screening Test results received anytime within the 2 years prior to randomisations must be repeated to ensure eligibility. Please refer to [Appendix H](#) for guidance.

Participants should have a Pap Smear or HPV Test at the end of treatment per local standard of care, if possible, between Week 48 and Week 52, to ensure that there is no evidence of new cervical dysplasia. Since access to a Pap Smear or HPV Test may vary by county, the Sponsor recommends that local guidelines for obtaining Pap Smear or HPV Test in participants who have received immunomodulators or immunosuppressive treatment be followed. If a Pap Smear was performed at the EOT was not normal but showed no evidence of malignancy (e.g., CIN III, CIS or AIS), it should be repeated as per the participant's gynaecologists recommendation. If the participant's gynaecologist has recommended a repeat Pap Smear be performed at a specified interval, the Pap Smear should be obtained as recommended and the report provided in source document.

Females aged < 25 years, who have never been sexually active or have well documented HPV vaccination records may not require a cervical cancer screening test.

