4.6.1 Exposure

4.6.1.1 Definition and Derivations

The duration of exposure to the IP per subject is defined as the number of days between the start and the end dates of IP plus the dosing frequency interval:

Duration of exposure (days) = (Last dosing date + 28 days) – first dosing date + 1.

The total year of exposure is the sum of duration of exposure (days) of all subjects in the respective treatment group divided by 365.25 (days/year).

The total number of infusions are counted per participant. Furthermore, the number of participants with an infusion are assessed in 4-weekly categories (i.e., 4 Weeks, 8 Weeks, 12 Weeks, ..., 52 Weeks). An infusion will be counted if it was given in the corresponding time window. Missed infusions are not counted. Additionally, the number of participants with duration of exposure longer than each of the 4-weekly categories (i.e., ≥ 4 weeks, ≥ 8 weeks, ≥ 12 weeks, ..., ≥ 52 weeks) will be presented. As the duration of exposure takes into account the total exposure time from the last dose + 28 days (as defined above), any missed or delayed infusions will contribute to exposure time, but not to the number of infusions. For example, if a participant interrupted treatment and received no infusion at week 4, he/she will be counted as "No infusion" at week 4, but is counted as having "Exposure ≥ 8 weeks" if he/she received an infusion at any time after Week 4.

The time to discontinuation of IP is the same as the duration of exposure.

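### HBV DNA monitoring of HBcAb-positive participants is not scheduled at the early discontinuation visit or in the Protocol 4.3.1 minimum list, so some early leavers miss a due test

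*Protocol*

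**What the plan says.** Exclusion criterion 11 (Protocol 3.2) rules out participants who are HBsAg positive, or HBcAb positive with HBV DNA above the quantitation limit. It admits HBcAb-positive participants below that limit and attaches a monitoring rule, which Table 4 footnote m repeats: "Participants who are HBcAb positive at screening will be tested every 3 months for HBV DNA". Both places add that levels must stay below the limit for the participant to remain eligible. Section 3.9 item 7 gives the matching reason to stop dosing: "Isolated HBc positivity with HBV DNA confirmed by the central laboratory".

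The Table 4 row carrying footnote m is marked at Weeks 12, 24, 36 and 48. It is blank at Week 52 and at EDV.

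Participants who stop investigational product are asked to keep attending every scheduled visit (3.9.3, 4.3.1). For those who decline, 4.3.1 says "the participant should complete the EDV within 4 weeks of the last dose of investigational medicinal product", followed by visits 8 and 12 weeks after the last dose. A further fallback covers those who refuse even that: "If the participant is unwilling to continue with any study visits, including EDV visit, at a minimum, the following assessments should be completed". The list that follows includes serum chemistry, haematology, urinalysis, complement, anti-dsDNA, and lipid and immunology profiles, but not HBV DNA. Table 5, whose second visit is at "12 weeks post last dose ±7D", has no HBV DNA row.

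**The concern.** The protocol chose HBV DNA as the monitoring test for a group it knowingly admits, and fixed the interval at 3 months. A participant who leaves the visit schedule early still gives blood at EDV or under the 4.3.1 list, yet HBV DNA is not among the tests on that blood. In Table 4 the other repeated safety-laboratory rows (chemistry with haematology and urinalysis, pregnancy test, QFT-G, immunology profile, lipid profile) are all marked at EDV. The HBV DNA row is the exception, which looks like an oversight.

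At stake is early detection of viral reactivation in an HBcAb-positive participant who has received up to three infusions with no test since screening, or whose 3-month test falls just as they leave. Without the test, detection rests on liver chemistry, which shows liver injury rather than viraemia. No efficacy analysis depends on this.

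**Working it through.** **Inputs**
- Dosing weeks: every 4 weeks from Week 0 to Week 48 (Protocol 1.4). Early last-dose weeks L are therefore 0, 4, ..., 44, which is 12 possibilities.
- Scheduled HBV DNA weeks: 12, 24, 36 and 48 (Table 4).
- Nominal EDV: L + 4. Section 4.3.1 sets 4 weeks as the limit, and 3.9.3 asks that the EDV follow the regular visit schedule where possible.
- Follow-up Visit 1: L + 8. Follow-up Visit 2: L + 12 (Table 5).
- Screening: up to 35 days, or 5 weeks, before Day 1.

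All figures are nominal and ignore the 7-day visit windows.

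**Step 1: reproduce the plan's schedule.** Reading 3 months as 12 weeks from Day 1 gives Weeks 12, 24, 36 and 48, which are the Table 4 marks.

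**Step 2: find where the next test falls for an early leaver.** Let T be the last scheduled test at or before L, with Day 1 = 0 if there is none. The next test is due at T + 12.

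| Last dose L | T | Due (T + 12) | Visit where it falls |
|---|---|---|---|
| 8, 20, 32, 44 | 0, 12, 24, 36 | 12, 24, 36, 48 | L + 4, the EDV |
| 4, 16, 28, 40 | 0, 12, 24, 36 | 12, 24, 36, 48 | L + 8, Follow-up Visit 1 |
| 0, 12, 24, 36 | 0, 12, 24, 36 | 12, 24, 36, 48 | L + 12, Follow-up Visit 2 |

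In 4 of the 12 early last-dose weeks the due test coincides with the nominal EDV, where it is not scheduled. If the EDV is held earlier than L + 4, the due date passes between EDV and Follow-up Visit 1, and the test is still not scheduled.

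**Step 3: find participants with no test after screening.** The first scheduled test is at Week 12. A participant last dosed at Week 0, 4 or 8 has a nominal EDV at Week 4, 8 or 12 and leaves the regular schedule there. That is 3 of the 12 last-dose weeks, after one, two or three infusions.

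**Step 4: check what a test at EDV would achieve.** The interval from T to the nominal EDV is L + 4 - T:
- 4 weeks for L = 0, 12, 24, 36;
- 8 weeks for L = 4, 16, 28, 40;
- 12 weeks for L = 8, 20, 32, 44.

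None exceeds 12 weeks. Counted from a screening sample up to 5 weeks before Day 1, the intervals for L = 0, 4 and 8 are up to 4 + 5 = 9, 8 + 5 = 13 and 12 + 5 = 17 weeks. The largest equals the 12 + 5 = 17 weeks already accepted between screening and Week 12 for someone who stays on schedule. The nominal EDV also falls at the end of exposure as SAP 4.6.1.1 counts it ("Last dosing date + 28 days"). That is an accounting convention, not evidence of a clinical risk window.

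**The case against.** The strongest objection is that footnote m covers the dosing period only. It sits on the treatment-period table, its next sentence concerns remaining eligible, and the matching action in 3.9 item 7 is stopping a drug that an early leaver has already stopped. On that reading nothing is missed. It does not fit the schedule, however: a participant who stops dosing but keeps attending is still tested at the remaining Table 4 visits. The row follows attendance, not dosing.

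Second, a participant last dosed at Week 8 who comes in at Week 12 could have the test done as an ordinary Week 12 assessment. That is true, and the miss arises only when the attendance is handled purely as an EDV. Marking the EDV column removes the dependence on that choice.

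Third, other safeguards exist, and this stands. Chemistry is done at EDV, at both follow-up visits and in the 4.3.1 list. The central laboratory alerts the investigator at ALT or AST of 3 times the upper limit of normal or bilirubin of 2 times (Appendix C 3). Section 5.2.1 allows extra samples. The Hy's Law kit (Appendix C 6) includes HBV DNA, recommended when IgG anti-HBc is positive, although that list is not mandatory.

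Fourth, support for the size of the risk is thin. The phrase "potential for viral reactivation due to blockade of the interferon pathway" in section 5.2.2.3 concerns papilloma virus and cervical dysplasia, and the same sentence reports no signal to date. Table 1 names "active HBV, HCV, CMV, or Epstein-Barr virus infection" as an entry exclusion, not as a reactivation risk calling for monitoring after dosing.

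**Conclusion.** The point holds as a minor patient-safety gap with a cheap remedy. For HBcAb-positive early leavers who decline regular visits, the protocol's own 3-month test is due at the nominal EDV and unscheduled for last dose at Week 8, 20, 32 or 44. No HBV DNA follows screening for last dose at Week 0, 4 or 8. This rests on a nominal EDV at last dose plus 4 weeks and on 3 months meaning 12 weeks. The number affected cannot be estimated, because the documents give no HBcAb prevalence.

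Two stronger readings are tempting but not supported. A reader might infer that the testing has no end point. Only the wording of footnote m and exclusion criterion 11 is silent; the Table 4 row ends at Week 48. A reader might also infer that omitting the test from Table 5 is itself an error, leaving gaps of 16 or 20 weeks to Follow-up Visit 2, or that completers lack a Week 60 test. That requires the 3-month rule to run through follow-up, which the documents do not state. For completers, Week 48 to Week 60 is 12 weeks, which does not exceed the interval.

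**What to change.** For HBcAb-positive participants:
- mark HBV DNA at EDV in Table 4;
- add HBV DNA to the minimum list in section 4.3.1;
- state in footnote m whether testing continues into follow-up. If it does, a test at Follow-up Visit 2 would go into Table 5. If not, that test is optional.

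This is one table mark, one list line and one footnote sentence, and can be carried in the next amendment. It adds one central-laboratory assay per affected participant, on blood already drawn at that contact, and none for completers or for those who keep attending. A follow-up test, if chosen, would be a further assay. Participants who accept only telephone follow-up would remain untested.
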